Title: Utility of Restrata With Split Thickness Skin Graft to Reconstruct the Forearm Donor Site

NCT Number: NCT04829331

ID: 21-RES-003

Document Date: 22 APRIL 2021

Title:

Utility of Restra (Acera Surgical Inc., St. Louis, MO) in forearm flap reconstruction with donor site healing and function.

Objective:

Understand association between use of Restra (Acera Surgical Inc., St. Louis, MO) in forearm flap reconstruction with donor site healing and function.

Hypothesis:

Use of Restra in combination with split-thickness skin graft for reconstruction of forearm flap reconstruction donor site will be associated with decreased occurrence of tendon exposure at four weeks post-operatively when compared to split-thickness skin graft alone.

Design:

Randomized controlled trial.

Setting:

Single institution, Nebraska Methodist Medical Center

Population:

Adult patients undergoing radial forearm free flap or ulnar forearm free flap at a single institution.

Intervention:

Reconstruction of forearm harvest site using Restra with a split-thickness skin graft.

Control:

Reconstruction of forearm harvest site using split-thickness skin graft alone.

Inclusion Criteria:

1. All patients age 19 or greater that will undergo radial forearm free flap or ulnar free flap.
2. Photo documentation of wound bed at two weeks and four weeks must be obtainable either by physician or patient.

Exclusion Criteria:

1. Active systemic immunosuppression (active use of high-dose steroids ($\geq 40\text{mg}$ prednisone daily or equivalent) or other immunosuppressive medications OR medical conditions causing immunosuppression, i.e. human immunodeficiency virus etc).
2. Diabetes mellitus with most recent Hemoglobin A1c ≥ 10.0 within 30 days prior to surgery.
3. Morbid obesity (BMI >40).
4. Inability to maintain wrist immobilization for full planned period.
5. Severe malnutrition (prealbumin levels <10 mg per dL within 30 days prior to surgery OR BMI <15 (very severely underweight)).
6. Other conditions felt to significantly impair wound healing per surgeon discretion.

Primary Outcomes:

1. Tendon exposure at four weeks post-operatively (Yes/No).

2. Percentage of surface area of split-thickness skin graft incorporation at four weeks post-operatively.

Secondary Outcomes:

1. Tendon exposure at two weeks post-operatively (Yes/No).
2. Percentage of surface area of split-thickness skin graft incorporation at two weeks post-operatively.

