3. Aesthetic appearance of donor site per surgeon rating (graded 1-10).
4. In patients with tendon exposure, time to complete wound epithelialization (measured as time from surgery to first documentation of complete epithelialization in days).
5. Need for re-operation on forearm or secondary wound care strategy after tendon exposure.
6. Forearm infection requiring surgical drainage and/or antibiotics.

Goal Enrollment:

40 total patients with 1:1 group enrollment. Power analysis was performed to identify necessary sample size to detect an absolute reduction of tendon exposure at four weeks of 15% (25% baseline, 10% expected rate with intervention with power of 80% and alpha 0.05). Under these assumptions, 100 patients would need to be recruited into each arm. Recent historical review of institutional volume demonstrates a rate of approximately 35 forearm flaps annually (2019-2020 data). Assuming a 70% study enrollment rate, we would meet enrollment goals in approximately eight years. This time commitment is felt by the study authors to exceed what is reasonable without first generating preliminary data. The proposed sample size is therefore practically derived based annual surgical volume at this institution and available resources from our industry partner. We recognize the limitations in this study, therefore, and that this design is not truly hypothesis testing. Using the above assumptions, we expect goal enrollment to be met within approximately 18 months.

Covariates Recorded:

1. Demographic data - Age, sex, race, ethnicity, BMI.
3. Medical history - Modified frailty index - 5, diabetes mellitus, coronary artery disease, peripheral artery disease, immunosuppression.
4. Social history - Smoking status (current/former/never, total py), alcohol use pattern
5. Wound surface area in square cm.

Randomization:

Occurs when the patient is scheduled for surgery. A simple randomization strategy will be utilized by creating a randomization list using <https://www.graphpad.com/quickcalcs/randomize1/>, which will ensure equal group distribution. The surgery scheduler will assign patients to their category based on this pre-determined list in consecutive order based on date of surgery scheduling request rather than surgical date to minimize risk of bias.

Consent:

Written informed consent will be obtained at the time of study enrollment and will be stored securely by the Methodist research office. This form is separately attached.

Protocol:

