1. All forearm and ulnar flaps will be harvested using a suprafascial harvest technique.
6. Surgical technique for application of Restrata with split-thickness skin graft.
 1. Restrata will be meshed in a 1:2 fashion to allow for egress of serous fluid and minimize risk of fluid collection.
 2. Restrata will be applied to the entire wound bed not amenable to primary closure and will be underlaid beneath the surrounding skin edges.
 3. A split-thickness skin graft is harvested from patient's thigh at 15:1000 inches and placed on top of the Restrata to cover the entire wound bed. The graft is sutured in place using suture choice of surgeon's preference.
 4. Ultrasound gel is applied to the graft and matrix.
 5. Xeroform gauze bolster is placed over the wound and secured using suture choice of surgeon's preference.
 6. The wrist is wrapped with kerlix gauze and the wrist is immobilized
7. Bolsters are removed at five days, the wound is inspected, and high-definition digital photographs are obtained.
8. The arm remains immobilized for two weeks, and daily xeroform dressing changes are performed by patients, family, or home health per treatment team discretion.
9. Immobilizers are removed at initial follow-up visit at two weeks and high-definition digital photographs are obtained. (Any visit between 12 and 16 days will be considered acceptable as two-week follow-up).
10. If graft incorporation is adequate at two-week follow-up per treating physician discretion, Vaseline® or alternative non-antibiotic ointment will be applied to the graft edges between two and four-week follow-up visits by patients, family, or home health per treatment team discretion. If graft failure occurs by two-week follow-up, Aquacel Ag (ConvaTec Medical Group. Deeside, UK) will be applied to the areas of graft failure as the primary treatment strategy with daily dressing changes.
11. High-definition digital photographs are obtained at four-week follow-up.
12. If graft incorporation is adequate at four-week follow-up per treating physician discretion, no additional wound care will be performed. If graft failure occurs by four-week follow-up, Aquacel Ag will be applied to the areas of graft failure as the primary treatment strategy with daily dressing changes.

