13. If at any point the treating physician feels that the primary treatment strategy is inadequate or inappropriate, a secondary wound care strategy (alternative treatment, negative pressure therapy, surgical debridement, repeat grafting, etc) may be pursued.
14. In any case of incomplete graft incorporation and/or tendon exposure, further photo documentation will be obtained by the patient, family, or home health or wound team, or physician until epithelialization is complete and further wound care is no longer needed. Details of continued follow-up visits and methods of further documentation will be individualized so as to minimize excessive demands on patient resources.
15. Photos of donor sites at each time period will be submitted for evaluation by two independent surgeons who possess expertise in evaluation of free flap donor site wounds and skin grafts but who will not be involved in enrollment of patients in this trial or of management of their wounds. The percentage of graft incorporation and presence or absence of tendon exposure will be documented by each physician in a blinded fashion. The independent surgeons will also rate donor site graft aesthetic appearance on a 1-10 scale in a blinded fashion. Time to

complete epithelialization will be determined by the treating physician, and photo documentation will be submitted for blinded review by the independent surgeons. Any case of failed epithelialization that does not completely epithelialize within 90 days after surgery will be categorized as “greater than 90 days for analysis”, and all study-related patient contact will cease at that time.

16. Descriptive statistics will be reported. Univariate statistics will be used to compare primary and secondary outcomes between groups.

Premature Termination of Study:

This study may be prematurely terminated by the study team at any point if outcomes appear unequivocally worse than standard of care, if unusual types or rates of complications occur, or if any other safety concerns arise. An interim analysis will be performed in order to assess comparative outcomes following successful treatment of 20 subjects and determine whether to proceed with the remainder of the study.

Variables:

1. Surgical harvest technique will not be standardized between surgeons with the exception of requiring suprafascial harvest overlying the area to be grafted.
2. Donor site of split-thickness graft will be at surgeon discretion.

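### Does the undefined phrase that triggers the interim look, after 20 successfully treated subjects, distort the look?

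*Protocol*

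**What the plan says.** Under Premature Termination of Study the protocol schedules one look: "An interim analysis will be performed in order to assess comparative outcomes following successful treatment of 20 subjects and determine whether to proceed" with the rest of the trial. The same paragraph gives a power that does not wait for the look: "This study may be prematurely terminated by the study team at any point if outcomes appear unequivocally worse than standard of care", with further grounds for unusual complications and other safety concerns.

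The passages that bear on when treatment ends or an outcome is known are these:

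- **Primary Outcomes:** "Tendon exposure at four weeks post-operatively (Yes/No") and the percentage of graft area incorporated, both at four weeks.
- **Protocol, item 12:** "If graft incorporation is adequate at four-week follow-up per treating physician discretion, no additional wound care will be performed".
- **Protocol, item 14:** after incomplete incorporation or tendon exposure, photographs continue "until epithelialization is complete and further wound care is no longer needed".
- **Protocol, item 15:** "Any case of failed epithelialization that does not completely epithelialize within 90 days after surgery will be categorized as" beyond 90 days, and study contact then stops.
- **Randomization:** "Occurs when the patient is scheduled for surgery", so being randomized and being treated are separate events.

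**The concern.** The trigger fixes a number but not an event, and three readings are possible.

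- **(a) Operation performed.** The most recent of the 20 would not yet have the four-week assessment on which both primary outcomes rest.
- **(b) Wound care finished.** Items 12, 14 and 15 end care at about four weeks for a good result and as late as 90 days for a poor one. Good results would enter the count sooner.
- **(c) Good outcome achieved.** Failures would not count towards the 20, so the date of the look would depend on the outcome being compared.

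The look decides whether the trial goes on, and few events are expected at it. With 10 subjects per arm and the planning rates in Goal Enrollment ("25% baseline, 10% expected rate with intervention with power of 80% and alpha 0.05"), that is 10 × 0.25 + 10 × 0.10 = 3.5 tendon exposures. One exposure left out is more than a quarter of them (1/3.5 = 29%).

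**Working it through.** **Inputs.** From Goal Enrollment: 40 patients, 1:1; exposure 25% with graft alone and 10% with the matrix; 35 flaps a year with 70% enrolled, so 35 × 0.70 = 24.5 subjects a year. The four-week and 90-day points are those given above. The planning figure reproduces: a two-sided 5% test of 25% against 10% with 80% power and no continuity correction needs 100 per arm, as stated. That figure does not bear on the trigger.

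**Reading (a).** Subjects operated on in the last 28 days: 24.5 × 28/365 = 1.9 of the 20. Waiting four weeks completes their data.

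**Reading (b).** Assumptions: a subject without exposure finishes at day 28. A subject with exposure finishes either uniformly between days 28 and 90 (31 days later on average) or always at day 90 (62 days later, an upper bound).

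Exposures seen at four weeks but not yet counted, at the average rate of 17.5%:

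- Uniform: 24.5 × 31/365 × 0.175 = 2.08 × 0.175 = 0.36
- Day 90: 24.5 × 62/365 × 0.175 = 4.16 × 0.175 = 0.73

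When 20 have finished, 20 plus that number have four-week data. Exposures among the 20 are therefore:

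- Uniform: 20.36 × 0.175 − 0.36 = 3.20, against 3.50 in 20 consecutive subjects
- Day 90: 20.73 × 0.175 − 0.73 = 2.90, against 3.50

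The chance that at least one known exposure is uncounted is about 1 − exp(−0.36) = 30% or 1 − exp(−0.73) = 52%. Simulation of 100,000 trials gives the same values (3.20 and 2.90; 30% and 52%). With 25% in both arms it gives 4.61 or 4.21 against 5.00, and 41% or 65%.

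The look compares arms, so the effect on the difference matters more than the pooled count. If only the 20 are analysed:

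| | Control | Matrix | Difference |
|---|---|---|---|
| Uniform | (10.18 × 0.25 − 0.26)/(10.18 − 0.26) = 23.0% | (10.18 × 0.10 − 0.10)/(10.18 − 0.10) = 9.1% | about 14 points |
| Day 90 | (10.36 × 0.25 − 0.52)/(10.36 − 0.52) = 21.0% | (10.36 × 0.10 − 0.21)/(10.36 − 0.21) = 8.2% | about 13 points |

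The planned difference is 15 points. Its standard deviation with 10 per arm is √(0.25 × 0.75/10 + 0.10 × 0.90/10) = 0.167, about 17 points (about 16 in simulation). The shift of 1 to 2 points is about an eighth of that at most.

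If instead all four-week data in hand are used, the uncounted exposures come back in and the expected difference stays at about 15 points.

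**Reading (c).** Take a good outcome as no exposure at four weeks. The look comes on average at about subject 20/(1 − 0.175) = 24.2, which is (24.2 − 20)/24.5 × 12 = 2.1 months later. The chance that 20 good outcomes never occur among 40 is below 0.01%.

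With control at 25% and other matrix rates:

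| Matrix exposure | Average position of look | Chance of no look |
|---|---|---|
| 25% | 26.7 | 0.02% |
| 38% (top of the published graft-failure range in Background Information, a proxy) | 29.1 | 0.4% |
| 50% (not in the protocol) | 31.6 | 3.3% |

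**The case for a change.** The strongest case for acting is that the protocol itself, not a later document, chose the word. It sets the number, the condition and the decision in one sentence, and the condition is unclear. Taking it as treatment completed does not settle the matter, because the protocol's own care rules end at times that depend on outcome. The power to stop at any time schedules no comparison, so this look is the only planned one, and naming a visit would cost nothing.

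What stands is that the wording is loose and names no visit. What does not stand is the step from there to a distorted look. The sentence says when to look, not whom to analyse. The losses under (b) need a restriction to the triggering 20 that appears nowhere, and the exposures concerned are by definition already known at four weeks. Item 14 also governs continued photographs rather than the end of the allocated treatment, which the protocol defines as the reconstruction itself. The model for (b) is simplified as well: subjects with incomplete incorporation but no exposure would also run late, which narrows the contrast it assumes. Which subjects enter an interim data cut is commonly settled in an analysis plan, and none is at hand here.

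**Conclusion.** No change follows. This is loose wording that analysts would fill sensibly: a look meant to compare outcomes halfway through 40 patients would be run on subjects who have their four-week results, whatever those results are. Done that way, the expected difference is unaffected.

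On the less favourable readings, the cost at the protocol's rates is small: about two subjects awaiting data for four weeks under (a), 1 to 2 points on a 15-point difference under (b), and a look about four subjects later under (c). A late or absent look becomes material only at a matrix exposure rate of about 50%, which the protocol does not contemplate and where the power to stop for harm already applies. The protocol also says in Goal Enrollment that the trial is not really a test of a hypothesis, so no formal error rate hangs on the exact timing.

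The figures assume steady accrual at 24.5 a year, the planning rates of 25% and 10%, tendon exposure as the mark of a poor outcome, and the healing times stated above, which the protocol does not give.
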